6.7 BASELINE, TIME WINDOWS AND CALCULATED VISITS

Values observed at Visit 1 during screening and enrollment will be considered as baseline assessment.

Enrolled patients will undergo two study visits. Visit 1 (baseline visit) and visit 2 (follow up visit) approximately at the 6 weeks (\pm 10 days of window period) after therapy with the product. A telephone contact will take place 2 weeks (\pm 10 days of window period) after first day of therapy to check for compliance and safety issues.

7 PLANNED ANALYSIS

- All study data will be included in individual patient study data listings. In general, all data will be listed by visit, study site and patients (wherever applicable). All summary tables will be presented with descriptive statistics for the parameters being analyzed, wherever applicable.
- Numeric presentations:
 - Non-integer numerical data should be presented with decimal point.
 - If the non-formatted data that are received (e.g., from the clinical database) are inconsistently presented, a decision on how to present the final data will be made on a case-by-case basis.
 - When rounding is required, number 5 or above will be rounded up.
 - When deriving new variable(s) based on raw data, no rounding will be performed at intermediate calculation. Rounding will only be performed when displaying data.
 - For End-Of-Text (EoT) tables, Descriptive analysis for continuous data will include number of non-missing observations (n), mean, standard deviation (SD), median, minimum and maximum. Means and medians will be rounded to 1 decimal place additional to the original data. Standard deviation will be rounded to 2 decimals place additional to the original data. Minimum and maximum will be displayed with the same decimal precision as the original data. Q1 and Q3 will be presented with 1 decimal additional to the original data.
 - For tables that are provided for primary and secondary outcomes with some extreme data, median, quartiles and percentiles should be preferred to mean, standard deviation, minimum and maximum.
 - Proportion and its confidence interval will be presented with 2 decimal places whenever applicable.

- Tabulations of frequencies for categorical data will include all possible categories and will display the number of observations in a category as well as the percentage (%) relative to the respective patient set whether they have non-missing values or not.
- Percentage should be displayed without the “%” sign within the data column. The precision for percentages should be one decimal point. The category missing will be displayed only if there are actually missing values.
- Zero count and percentage will be presented as ‘0’ only.
- Missing data will not be imputed but will be analyzed as missing.
- Baseline assessments are the assessments taken at the visit 1 for all patients. If there are multiple assessments collected on the same scheduled time, the average of these assessments will be used.
- The change from baseline is defined as the post-baseline value minus the baseline value.
- Text column should be left justified.
- All the data analysis will be done using SAS® version 9.2 or higher.

7.1 DEMOGRAPHIC AND OTHER BASELINE CHARACTERISTICS

Demographic and other baseline characteristics at visit 1 (baseline) will be listed individually by study site and patients and only descriptive statistics are planned for the demographic and baseline characteristics.

Age, age at start of COPD, height, weight, number of exacerbation in the last 12 months, number of exacerbation leading to hospitalization in the last 12 months and number of pack-years will be summarized using descriptive statistics and gender (male and female), pregnancy status (pregnant, not pregnant and not applicable), number of exacerbation in last 12 months (0, 1 and ≥ 2), number of exacerbation leading to hospitalization in the last 12 months (0, 1 and ≥ 2), smoking status (smoker, ex-smoker, nonsmoker), Spirometric COPD severity (GOLD spirometric classification 1, 2, 3, 4), COPD severity (GOLD patients group B, C, D and mMRC score will be summarized using frequency counts and percentages.

Table 7.1: 1 Breathlessness based on mMRC scale

mMRC scale	Breathlessness condition
Grade 0	I only get breathless with strenuous exercise.
Grade 1	I get short of breath when hurrying on the level or walking up a slight
Grade 2	On level ground, I walk slower than people of the same age on the level because of breathlessness, or I have to stop for breath when walking on my own pace.
Grade 3	I stop for breath after walking about 100 yards (about 91 meters) or after a few minutes on the level ground.
Grade 4	I am too breathless to leave the house or I am breathless when dressing.

7.2 CONCOMITANT DISEASES AND MEDICATION

Relevant past and concomitant medical conditions/ diseases/ comorbidities and concomitant medication will be listed individually by site and patients.

All the past and concomitant medical conditions/ diseases/ comorbidities will be coded using MedDRA, version 20.1 or higher.

Patients used other COPD related therapeutics in last 6 months prior to treatment will be listed individually by site and patients separately.

Medication used before the first dose of Spiolto® Respimat® will be considered as prior medication and medication used after the first dose or medication used during the study duration will be recorded as concomitant medications.

All prior or concomitant medications will be coded using the World Health Organization Drug Dictionary (WHO DD), enhanced version September 2017 or later, and will be summarized using frequency counts and percentages as per ATC level 3 text.

7.3 TREATMENT COMPLIANCE

No analysis planned for compliance of treatment.

7.4 PRIMARY OUTCOME

The primary outcome is to measure the proportion of patients achieving the “therapeutic success” defined as a ≥ 0.4 point of decrease in the Clinical COPD Questionnaire (CCQ) score between visit 1 (baseline) and visit 2 (approximately 6 weeks \pm 10 days after visit 1). A change of ≥ 0.4 points (decrease) is considered to be the minimal clinically important difference (MCID) for both CCQ score and CCQ-4.

CCQ is short questionnaire with 10 questions (regards to their symptoms, functional and mental state) and that is scored by the patient on a 7-point scale between 0 (very good health status) and 6 (extremely poor health status) at visit 1 (baseline) and visit 2 (end of the observation approximately 6 weeks \pm 10 days after visit 1). A higher score is indicative of worse status.

CCQ questionnaire is subdivided into three domains and rules required to calculate CCQ score is given as below in table 7.4:1.

Table 7.4: 1 Rules to calculate the CCQ score

Domain	Questions number*	Number of questions in domain	Number of questions required	% Required questions
Symptoms	1, 2, 5 and 6	4	3	75
Functional state	7, 8, 9 and 10	4	3	75
Mental state	3 and 4	2	2	100

*Refer annex.3 of protocol i.e. additional information of protocol for Clinical COPD Questionnaire.

Individual questions within the CCQ are equally weighted.

Total CCQ score can be calculated if the number of required questions per each domain is available and individual domain specific CCQ scores are calculable.

Suppose scores for all the domain specific questions are available except one question with missing score in the functional status domain and/or symptom domain. So, functional status domain and symptom domain specific CCQ score can be calculated as per the rule though it has missing data. Hence, total CCQ score also can be calculated.

Domain specific CCQ score is calculated as below:

$$\text{Domain specific CCQScore} = \frac{\text{Sum of available scores for domain specific questions}}{\text{Number of non - missing questions for specific domain}}$$

The total CCQ score is calculated by adding the score of the ten questions divided by 10 or by multiplying the domain specific score with the original amount of questions and adding these numbers and dividing by 10 as below:

$$\text{Total CCQScore} = \frac{[(\text{Symptom domain score} \times 4) + (\text{Functional state domain} \times 4) + (\text{Mental state domain} \times 2)]}{10}$$

For example, when question #5 is not completed or there are two answers, the scores will be calculating as follows:

For the symptom domain, add the score from questions 1, 2 and 6 and divide by 3. Calculate the other domain scores as usual. To calculate the total score use the following algorithm mentioned above i.e.

$$\text{Total CCQScore} = \frac{[(\text{Symptom domain score} \times 4) + (\text{Functional state domain} \times 4) + (\text{Mental state domain} \times 2)]}{10}$$

Handling of the missing value or ambiguous values will be handled as specified in TSAP [section 6.6](#).

The proportion of patients with therapeutic success (≥ 0.4 point decrease in total CCQ score from visit 1 to visit 2) at visit 2 will be presented with the 95% confidence interval.

The 95% confidence interval will be estimated using Clopper Pearson Exact method.

The following SAS program or other relevant program can be used to estimate the proportion and its related confidence interval.

```
proc freq data=<data-set>;
by <variable>;
tables <variable>/ binomial;
exact binomial;
run;
```

Also prepared Bar Graph of Number and Percentage of subjects achieved therapeutic success.

Subgroup analysis will be performed for primary outcome as per mentioned in the TSAP [section 6.4](#).

7.5 SECONDARY OUTCOMES

7.5.1 Secondary outcomes

- The CCQ scores and CCQ-4 scores at both the visits and absolute change in the CCQ and CCQ-4 score from visit 1 to visit 2 will be summarized with descriptive statistics (n, mean, SD, maximum, median, minimum). The summary for the same will be presented for the patients with therapeutic success (i.e. ≥ 0.4 point decrease in CCQ score between visit 1 and visit 2. Also prepared Bar Graph of Absolute change in Total CCQ and CCQ-4 Score.
CCQ-4 is the functional status subdomain of CCQ. The functional status (CCQ-4) is calculated as sum of the 4 questions i.e. question number 7, 8, 9 and 10 divided by 4. Additionally, subgroup analysis will be performed as specified in [section 6.4](#).
- The Physician's Global Evaluation (PGE) assesses the patients general condition using and eight-point scale ranging from 1 (poor) to 8 (excellent). The Physician's Global Evaluation (PGE) score at visit 1 and visit 2 will be listed individually by site, patients and visit and summarize by frequency count and percentage. Additionally, the shift from baseline table will be prepared for the PGE score and also prepared the Bar graph.
- Patient satisfaction with Spiolto® Respimat® will be evaluated at visit 2 using seven point ordinal scale ranging from very dissatisfy to very satisfied of abbreviated PASAPQ Part-I questionnaire. Patients satisfaction with Spiolto® Respimat® at visit 2 (end of the study) will be listed individually by site and patients and summarize by frequency count and percentage also prepared Bar Graph of Patients Satisfaction Score (PASAPQ Part I) at Visit 2.
- Patient preference (PASAPQ part-II: Rating of preference and willingness to continue with inhaler) at visit 2 (end of the study) for the patients who have used the Spiriva HH prior to the study will be listed individually by site and patients and summarize by frequency and percentage and also prepared Bar Graph of Patients' (who have used

Spiriva HH prior to the study) Preference and Willingness to Continue with Inhaler (PASAPQ Part II) at Visit 2.

- Patients' willingness score to continue using Spiolto® Respimat® inhaler device at visit 2 for the patient who have used Spiriva HH prior to the study will be listed individually by site and patients and summarize by descriptive statistics. Patients' willingness score will range from 0 to 100. 0 indicated patient would not be willing to continue using Spiolto® Respimat® inhaler and 100 indicates patient would definitely be willing to continue Spiolto® Respimat® inhaler.
- Treatment continuation of Spiolto® Respimat® after the study will be measured based on the Yes/No question if treatment with Spiolto® Respimat® is going to be continued after the study. Percentage of patients willing to continue with Spiolto® Respimat® after the study will be summarized.

All the analysis related to primary and secondary outcomes will be carried out on full analysis set (FAS).

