Rational for Spiolto® Respimat® treatment discontinuation (if applicable)		X	X
Continuation or discontinuation of treatment with Spiolto® Respimat® after the study (yes/no)		X	X

GOLD patient group (B, C or D) will be automatically calculated within the eCRF based on available exacerbation history, mMRC and GOLD spirometric classification of airflow limitation based on post-bronchodilator FEV₁ if available.

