9.2.3 Study visits

Enrolled patients will undergo 2 study visits. Visit 1 (baseline visit) during screening and enrollment, visit 2 (follow up visit) at the end of 6 weeks therapy with the product. A telephone contact will take place 2 weeks after first day of therapy to check for compliance and safety issues.

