9.7 DATA ANALYSIS

All patients who have received at least one dose of Spiolto® Respimat® will be included in the analyses; this is the treated set. All analyses will be performed on the treated set (as treated analysis). If patients have missing values for an outcome, those patients will be excluded for that outcome's analysis. For example, if a patient is missing the CCQ score at Visit 1 and/or Visit 2, that patient will be excluded from the analyses for the primary endpoint of therapeutic success and the secondary endpoint of change in CCQ from Visit 1 to Visit 2.

The statistical characteristics presented in the end-of-text tables will be N / mean / SD / min / median / max for continuous variables. Tabulations of relative and absolute frequencies will be presented for categorical variables. Proportion and 95% CI will be given when appropriate.

The analyses will relate to the following data:

- Patient demographics (age, gender, height, and weight).
- Comorbidities (main diagnosis and concurrent diagnosis according to MedDRA, version valid as at the time of database closure).
- COPD related and other concomitant medication (according to the WHO classification, version valid at the time of database closure).
- History of smoking.
- Exacerbations.
- Breathlessness based on mMRC score at Visit 1.
- Physical Functioning based on CCQ scores (therapeutic success at Visit 2); primary outcome.
- Changes from Visit 1 to Visit 2 in the CCQ score; secondary outcome.
- Changes from Visit 1 to Visit 2 in the CCQ-4 score (subdomain of the CCQ); secondary outcome.
- Patient satisfaction with Spiolto® Respimat® and device preference for those patients that used Spiriva HH previous to the study, at Visit 2 only; secondary outcome.
- Treatment continuation of Spiolto® Respimat® after the study; secondary outcome
- General condition of the patient: evaluated by the physician (Physician's Global Evaluation (PGE)); secondary outcome.
- Adverse Drug Reactions (ADR & SADR), fatal AEs, pregnancies.
- GOLD spirometric classification (1,2, 3, 4), if available.
- GOLD patient groups (B, C, D).
- Details of treatment with inhaled respiratory agents before the study.
- Details of treatment with respiratory agents during the study
- Reasons for ending treatment during the observation period
- Details of treatment continuation / discontinuation

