6.3 PATIENTS SET ANALYSED

➤ **Enrolled Set:**

Enrolled set include all screened patients with the informed consent and date of registration.

➤ **Treated Set (TS):**

Treated set include all screened patients with the informed consent, date of registration and at least one documented administration of Spiolto® Respimat®.

➤ **Full Analysis Set (FAS):**

Full analysis set include all screened patients with informed consent, date of registration, at least one documented administration of Spiolto® Respimat® and available total CCQ score at visit 1 and visit 2.

If patients have missing values for an outcome, those patients will be excluded for that outcome's analysis as specified under [section 6.6](#).

The below table 6.3:1 explains the patient analysis set to be used for each planned analysis

Table 6.3: 1 Patients sets analysed

Class of outcomes	Patient set		
	Enrolled set	Treated set	Full analysis set
Primary and key secondary outcomes	-	-	X
(Other) Secondary and further outcomes	-	-	X
Safety endpoints	-	X	-

Class of outcomes	Patient set		
	Enrolled set	Treated set	Full analysis set
Demographic/baseline outcomes	-	X	-
Disposition/inclusion exclusion criteria and important protocol violation	X	-	-

Note: No key secondary and further outcomes mentioned in CTP.

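### Treatment continuation is analysed only in patients with a CCQ total at both visits, so recorded early stops can drop out and the rate can be overstated

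*SAP*

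**What the plan says.** **Outcome.** SAP 7.5.1 states that continuation "will be measured based on the Yes/No question if treatment with Spiolto® Respimat® is going to be continued after the study". The output is described as follows: "Percentage of patients willing to continue with Spiolto® Respimat® after the study will be summarized".

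**Analysis set.** The same section closes with "All the analysis related to primary and secondary outcomes will be carried out on full analysis set (FAS". Under SAP 6.3 the FAS takes treated patients who also have an "available total CCQ score at visit 1 and visit 2". Protocol 9.7 differs: every analysis uses the treated set (at least one dose), and a patient leaves an outcome's analysis only if that outcome is missing. SAP 4, on changes to the planned analysis, does not mention the move to the FAS.

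**Collection.** Protocol Table 9.1.1 lists "Continuation or discontinuation of treatment with Spiolto® Respimat® after the study (yes/no" and marks it both at Visit 2 and at the telephone contact. The reason for discontinuation is marked at the same two points. Protocol 9.2.3 describes the call: "A telephone contact will take place 2 weeks after first day of therapy to check for compliance and safety issues". SAP 5.4 adds withdrawal from treatment since baseline, collected at Visit 2.

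**Denominator.** SAP 7 takes categorical percentages over the whole patient set, including members with missing values. SAP 6.3 removes patients with a missing value from that outcome's analysis.

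**Stopping more generally.** Protocol 9.7 includes "Reasons for ending treatment during the observation period" among the data to be analysed.

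**The concern.** For the CCQ change, a patient who leaves early has a missing value. For continuation, a patient who has stopped has a known value: not continuing. Requiring a completed Visit 2 CCQ therefore selects on something closely tied to the result. Recorded stoppers who do not return, or who return without a calculable CCQ total, are lost even though their status is on file.

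The figure would be read as the share of patients started on Spiolto who go on with it. As specified, it is the share among those who stayed long enough, and answered fully enough, to have two CCQ totals. The word willing blurs this further, because the item records whether treatment is to be continued, not an attitude.

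**Working it through.** **1. Inputs.** From protocol 9.5: 1170 evaluable patients, 10% drop-out, 1300 in total. The documents give no expected continuation rate and no number of stoppers without a Visit 2 CCQ, so both are assumed and varied below.

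**2. The plan's own figures.** 1170 / (1 − 0.10) = 1300, as stated. At 50% success, 0.5 ± 1.96 × √(0.25/1170) gives 47.1% to 52.9%, also as stated. There is no planned figure for continuation to reproduce.

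**3. Tracing treated patients through the SAP.**

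| Patient | In FAS? | Counted in SAP 7.5.1 | Known status |
|---|---|---|---|
| Stop recorded at the call, does not return | No | Not at all | Not continuing |
| Stopped, answers No at Visit 2, one mental-state CCQ item blank | No (total not calculable, SAP 6.6) | Not at all | Not continuing |
| Stopped, answers No at Visit 2, CCQ complete | Yes | As No | Not continuing |
| CCQ complete, continuation item blank | Yes | In the denominator under SAP 7, removed under SAP 6.3 | Unknown unless a stop is recorded |

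The first two rows are the problem. Neither denominator rule reaches them, because both rules act inside the FAS.

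**4. Formula.** Let F be the FAS size, O the treated patients outside it, c the Yes rate in the FAS, and s the share of O with a recorded stop. The reported rate is c. Counting recorded stops as No, among patients of known status, gives cF/(F + sO). The overstatement is the difference, c × sO/(F + sO).

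**5. Results** for F = 1170, O = 130, c = 95%, so cF = 1111.5:

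| s | Rate with stops counted | Overstatement |
|---|---|---|
| 0 | 1111.5/1170 = 95.0% | 0 |
| 25% | 1111.5/1202.5 = 92.4% | 2.6 points |
| 50% | 1111.5/1235 = 90.0% | 5.0 points |
| 100% | 1111.5/1300 = 85.5% | 9.5 points |

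**6. Sensitivity.** At s = 100% the overstatement is c × O/1300. With 10% outside the FAS this is 8.0, 9.0 or 9.5 points for c = 80%, 90% or 95%. With 5% outside it is 4.0 points (0.80 × 5) to 4.75 (0.95 × 5). With 15% outside it is 12.0 to 14.25. At s = 0 it is always 0.

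**7. The same cases with all 1300 as denominator.** Continuing is 1111.5/1300 = 85.5% throughout. FAS patients answering No number 1170 − 1111.5 = 58.5. Not continuing is (58.5 + 130s)/1300 and unknown is 130(1 − s)/1300:

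| s | Not continuing | Unknown |
|---|---|---|
| 0 | 4.5% | 10.0% |
| 25% | 7.0% | 7.5% |
| 50% | 9.5% | 5.0% |
| 100% | 14.5% | 0% |

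The 85.5% must therefore be read beside the unknown row.

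**The case against.** The strongest reply is that the question itself is sound. A reader might infer that it is put only at Visit 2, so that a stop reported by telephone can never count. Table 9.1.1 does not support that: the item is marked at the call too, and the SAP's continuation bullets, unlike its bullets on satisfaction, preference and willingness, do not say at Visit 2. A telephone No is an answer, not a missing value. It follows that returning to the treated set under protocol 9.7 would largely cure the problem; the claim that it would not help does not hold. What stands is that the FAS removes such patients, and that no readable SAP rule says which answer prevails or how to treat a stop recorded only through its reason.

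A reader might also infer that inflation is certain, or that stops for lack of effect or dislike of the device are the ones lost. Neither is shown. Withdrawal and reasons are also collected at Visit 2, so stoppers may attend, and the documents do not describe those who do not.

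Nor is stopping invisible in the SAP. Section 7.7 summarises days on treatment, Table 6.3:1 assigns disposition to the enrolled set, and section 7 promises listings of all study data. What the readable text lacks is a dedicated summary of reasons for ending treatment; some SAP sections cannot be read.

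Finally, this is a descriptive secondary outcome with no test or threshold attached. That limits its weight but does not justify conditioning it on the CCQ.

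**Conclusion.** The point holds in this form: the FAS restriction, contrary to protocol 9.7, can remove patients whose continuation status is known, and no readable rule restores them. The effect is upward whenever the excluded patients of known status continue less often than FAS patients, as recorded stoppers do by definition.

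The size is open. The illustration assumes that all 1300 are treated, that the whole 10% drop-out falls outside the FAS, and that every FAS patient has an answer. It also assumes that nobody outside the FAS answered Yes at Visit 2; such patients would pull the other way. The upper end needs every one of the 130 to have a recorded stop, which is a bound and not an expectation.

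The denominator conflict and the missing rule for combining answers are separate gaps and stand whatever the size. The change should be made; the primary outcome is not affected.

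**What to change.** In SAP 5.2.1, Table 6.3:1 and 7.5.1, analyse continuation on the treated set, with all treated patients as the denominator, and state that this rule overrides the general ones in SAP 6.3 and 7. Define three categories:

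- **Not continuing:** any Spiolto stop recorded at the 2-week call or up to Visit 2 (through the yes/no item, the reason or the withdrawal record) without recorded resumption, or No at Visit 2.
- **Continuing:** Yes at Visit 2 and no such unresumed stop.
- **Unknown:** no recorded stop and no Visit 2 answer, shown as its own row. A telephone Yes with no Visit 2 answer falls here.

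Label the result planned continuation rather than willingness. Optionally, add a treated-set table of reasons for ending treatment, which protocol 9.7 lists for analysis.

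The cost is SAP wording and one derived variable, plus one table if the option is taken, all from data that the protocol already collects. The downside is a possibly less favourable figure and a visible unknown row.

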4 CHANGES IN THE PLANNED ANALYSIS OF THE STUDY

As per amended protocol version 2.0, dated 28th Aug 2018, the statistical changes include change in CCQ score calculation (Section 9.8.3) and inclusion of secondary outcome “Treatment continuation of Spiolto® Respimat® after the study” (Section 9.3.2.2).

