6.6 HANDLING OF MISSING DATA AND OUTLIERS

The questions in Clinical COPD Questionnaire (CCQ) are divided into symptoms based, function state and mental state domains. Total CCQ score with missing data can not be calculated if domain specific CCQ score are not calculable as per the rule specified in TSAP section 7.4.

When a data is ambiguous (e.g. if patient fills in two answers on one question), the data should be considered as missing.

For example, when one question in mental state domain has missing or ambiguous score, then CCQ score for mental state domain can not be calculated. Hence, total CCQ score can not be calculated and will be considered as missing.

Other missing values will be considered as missing, no imputation will be done for the analysis purpose.

Missing or incomplete AE dates are imputed according to BI standards⁽²⁾ (i.e. “Handling of missing and incomplete AE dates”).

No outlier analysis is planned for this study.

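### The SAP restricts every secondary outcome to patients with a total CCQ score at both visits, where the protocol uses the treated set outcome by outcome; the departure is neither stated nor justified

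*SAP*

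**What the plan says.** **Protocol.** Section 9.7 says "All analyses will be performed on the treated set (as treated analysis", the treated set being patients with at least one dose. It then sets the missing-data rule: "If patients have missing values for an outcome, those patients will be excluded for that" outcome's analysis. Its worked example confines exclusion for a missing CCQ score to therapeutic success and change in CCQ. The same section lists CCQ-4, PGE, satisfaction and preference, and treatment continuation among the analyses. The protocol defines no full analysis set.

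**SAP.** Section 6.3 defines the FAS as consented, registered patients with "at least one documented administration of Spiolto® Respimat® and available total CCQ score at visit 1 and visit 2". Table 6.3:1 assigns primary and secondary outcomes to it, and 7.5.1 closes with "All the analysis related to primary and secondary outcomes will be carried out on full analysis set (FAS". Section 6.3 repeats the outcome-by-outcome exclusion sentence. Section 4, on changes to the planned analysis, says "the statistical changes include change in CCQ score calculation (Section 9.8.3) and inclusion of secondary outcome" of treatment continuation. It does not mention the analysis set.

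**Scoring.** If one of the two mental-state items is missing or double-marked, SAP 6.6 concludes: "Hence, total CCQ score can not be calculated and will be considered as missing". For a single gap in another domain, SAP 7.4 says "So, functional status domain and symptom domain specific CCQ score can be calculated as per the rule though it has missing data". SAP 7.5.1 notes that "CCQ-4 is the functional status subdomain of CCQ", built from items 7 to 10 only.

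**The concern.** The two documents give different populations for most secondary outcomes. The outcome-by-outcome sentence in SAP 6.3 does not close the gap: it can remove patients from the FAS but cannot bring back anyone already outside it.

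A patient can lack a total CCQ for reasons unrelated to the other outcomes. CCQ-4 contains no mental-state item, PGE is completed by the physician, and PASAPQ is a separate form. Protocol Table 9.1.1 also marks continuation (yes/no) at the 2-week telephone contact as well as at visit 2, so an answer may exist for someone with no visit-2 CCQ.

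What is at stake is the use of collected data that the protocol says will be summarised, and agreement between protocol and SAP on most secondary outcomes. CCQ-4 has some weight here, because both documents describe functional status as the study's specific interest.

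**Working it through.** **1. The plan's own figures.** Protocol 9.5 gives 1170 evaluable patients, a 50% success rate and 10% drop-out.
- 95% CI: 0.50 ± 1.96 × √(0.25/1170) = 47.13% to 52.87% (stated 47.1% to 52.9%).
- Enrolment: 1170/(1 − 0.10) = 1300, as stated.

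Neither figure changes. Treated patients with total CCQ at both visits are exactly the FAS, so the primary outcome and change in total CCQ use the same people under both documents.

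**2. Which outcomes differ.**

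| Outcome | Protocol 9.7 needs | SAP needs | Same patients? |
|---|---|---|---|
| Therapeutic success, change in total CCQ | total CCQ at both visits | the same | yes |
| CCQ-4 | CCQ-4 | CCQ-4 and total CCQ at both visits | no |
| PGE | PGE | PGE and total CCQ at both visits | no |
| PASAPQ Part 1; preference and willingness (prior HandiHaler users) | the PASAPQ answer | the answer and total CCQ at both visits | no |
| Continuation | a recorded yes/no | a recorded yes/no and total CCQ at both visits | no |

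**3. Illustration for CCQ-4.** Assume each item is unscorable with probability m, independently, at each visit. None of the m values comes from the documents. Take 1170 as the number attending both visits.
- A four-item domain is scorable with at least 3 items: d = (1 − m)^4 + 4m(1 − m)^3.
- The mental-state domain is scorable with both items: (1 − m)^2.
- Functional domain scorable at both visits: d^2.
- Total CCQ scorable at both visits: (d × d × (1 − m)^2)^2 = d^4 (1 − m)^4.
- Left out although the functional domain is scorable: 1170 × [d^2 − d^4 (1 − m)^4].

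| m | d^2 | total at both visits | left out of 1170 |
|---|---|---|---|
| 0.5% | 0.9997 | 0.9796 | 23.6 |
| 1% | 0.9988 | 0.9583 | 47.4 |
| 2% | 0.9953 | 0.9138 | 95.4 |

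(Last column from unrounded probabilities.) If CCQ-4 needed all four items, the expression is 1170 × (1 − m)^8 × [1 − d^2 (1 − m)^4], giving about 23, 44 and 82. The point therefore does not depend on the 3-of-4 rule.

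**4. Continuation.** Let k be the number outside the FAS who have a recorded answer, p_F the share answering yes in the FAS, and p_K the share answering yes among the k. With 1170 now taken as the FAS size:

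FAS percentage − treated-set percentage = [k/(1170 + k)] × (p_F − p_K).

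The sign is that of p_F − p_K, and the documents give neither share, nor k. For example, assume p_F = 95% and k = 65 (half of the 130 planned drop-outs). The factor is 65/1235 = 0.0526. The difference is then +5.0 points if all 65 said no, and −0.3 if all said yes. With k = 0 it is zero. This shows only that the sign is open; it does not estimate an effect.

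Steps 3 and 4 use 1170 in different senses (attenders, then FAS size) and should not be combined.

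**The case against.** The strongest reply has four parts.

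- **Disclosure.** SAP section 4 reports what the protocol amendment changed and says the changes *include* two items, so it need not be exhaustive. The FAS is openly defined in 6.3, tabulated and restated in 7.5.1. This stands against any inference that the restriction was concealed. It does not supply a statement that the protocol's set has been replaced, or a reason. The SAP history table logs an analysis-set update, but only between SAP drafts.
- **Continuation.** SAP 7.5.1 asks about treatment after the study, which reads as an end-of-study question, and the 2-week call is described as a check on adherence and safety. Leaving the FAS depends on missing CCQ, not on stopping treatment: someone who stopped but completed a scorable CCQ at visit 2 stays in, and the no counts. A reader might infer that the FAS must inflate the continuation percentage. The documents do not support that, because the answers of the excluded patients are unknown and the sign can go either way. Counting a week-2 yes from a patient later lost as continuation after the study could itself inflate the figure.
- **Numbers.** Item missingness and independence are assumed, and the eCRF checks in protocol 9.6 and 9.8 may make missing items rarer. This stands: the counts are illustrative.
- **Consequence.** The secondary analyses are descriptive, all data stay in patient listings, and disposition, exposure and adverse-event discontinuation outputs show withdrawals. This limits the harm but does not change the populations behind the secondary summaries.

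**Conclusion.** The conflict is established from the text: protocol 9.7 and SAP Table 6.3:1 with 7.5.1 give different populations for CCQ-4, PGE, PASAPQ Parts 1 and 2, willingness and continuation, and SAP section 4 neither states nor justifies the difference. The primary outcome and change in total CCQ are untouched.

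The consequence is unnecessary loss of usable data from the summaries. For CCQ-4 it is about 24, 47 or 95 of 1170 attenders, resting wholly on the assumed 0.5%, 1% or 2% independent item missingness. No bias is shown for CCQ-4, PGE, satisfaction, preference or willingness. For continuation, patients with a recorded answer but no total CCQ leave both numerator and denominator; the size and direction of the effect are not determinable from the documents. The point should be fixed, but it does not threaten the study's main result.

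**What to change.** In SAP Table 6.3:1 and 7.5.1:

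- Keep the FAS for therapeutic success, change in total CCQ, and any summary restricted to patients with therapeutic success (7.5.1 plans such summaries for CCQ and CCQ-4).
- Analyse CCQ-4 (visit values and change), visit-level total CCQ, PGE, PASAPQ Parts 1 and 2, willingness and continuation on the treated set, each with its own available data, as protocol 9.7 says.
- Reconcile the CCQ-4 formula in 7.5.1, which divides the four-item total by 4, with the 3-of-4 domain rule in Table 7.4:1.
- For continuation, report yes, no and unknown on the treated set. Make visit-2 answers the main result and show answers available only from the 2-week call separately, treating yes and no alike.
- List any remaining departure from protocol 9.7 in SAP section 4, with the reason.

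The cost is SAP wording and a change of population flag. Denominators will differ between outcomes, and the continuation percentage may become less favourable.
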